1.1 Overview of Neuroendocrine Tumors

Neuroendocrine tumors are a heterogeneous group of neoplasms which include carcinoid tumors and pancreatic neuroendocrine tumors. The majority are characterized by a relatively indolent rate of growth and a propensity to produce and secrete a variety of hormones and other vasoactive substances, giving rise to diverse clinical syndromes. Histologically, carcinoid tumors arise from the endocrine (enterochromaffin) cells of the gastrointestinal tract and airways. Carcinoid tumors have distinct features depending on their site of origin. In the 1960s, Williams et al classified carcinoid tumors based on embryologic derivation, distinguishing between foregut (bronchial, stomach, duodenal), midgut (jejunal, ileal, cecal, appendiceal) and hindgut (distal colon and rectal) tumors.¹ As a rule of thumb, metastatic midgut carcinoid tumors produce serotonin and other vasoactive substances which give rise to the typical carcinoid syndrome.² This syndrome manifests primarily as diarrhea and flushing, a vasomotor phenomenon which causes redness and warmth in the face and upper torso. Carcinoid heart disease, characterized by fibrosis of the tricuspid and pulmonic heart valves, can also occur in patients with severe and prolonged elevations of circulating serotonin. In contrast, hindgut carcinoid tumors are rarely, if ever, associated with a hormonal syndrome. Tumor growth rates also correlate with site of origin. In the metastatic setting, midgut carcinoid tumors tend to behave in the most indolent fashion, whereas neuroendocrine tumors originating in the foregut or hindgut regions tend to behave more aggressively once they have metastasized.

Pancreatic neuroendocrine tumors arise from the islets of Langerhans. These heterogeneous neoplasms can secrete a variety of peptide hormones, including insulin, gastrin, glucagon, and vasoactive intestinal peptide (VIP).² In contemporary studies, most pancreatic neuroendocrine tumors are unassociated with a hormonal syndrome, and are termed “nonfunctioning.”

Treatment options for metastatic neuroendocrine tumors have evolved in recent years. Somatostatin analogs such as octreotide were initially developed to palliate hormonal symptoms such as the flushing and diarrhea caused by the carcinoid syndrome.³ More recently, accumulating data has supported their role as antiproliferative agents, capable of stabilizing tumor growth in patients with metastatic neuroendocrine malignancies.⁴ Last year, results of a phase III, randomized, placebo-controlled trial were published, demonstrating that long-acting octreotide (Sandostatin LAR 30 mg) significantly prolonged time to tumor progression among patients with metastatic midgut carcinoid tumors.⁵

Emerging evidence supports the use of other targeted agents, although none yet is considered standard of care. Sunitinib, a multitargeted tyrosine kinase receptor inhibitor, has recently been demonstrated to prolong progression-free survival in patients with metastatic pancreatic neuroendocrine tumors. Everolimus, an inhibitor of mammalian target of rapamycin (mTOR) has shown promise in several phase II studies.⁶ Results of randomized, placebo-controlled phase III studies are pending. Bevacizumab, an inhibitor of circulating vascular-endothelial growth factor (VEGF) is also being tested in phase III studies based on encouraging phase II

evidence. Cytotoxic chemotherapy appears to produce high response rates in metastatic pancreatic neuroendocrine tumors⁷; however responses in carcinoid tumors have been discouraging.

Among the various emerging treatments, somatostatin analogs appear to be associated with the most favorable side effect profile and ease of administration. Their convenient mode of administration and tolerability are particularly important in patients with metastatic neuroendocrine tumors who often remain on treatment for many years.

1.2 Somatostatin analogs in the treatment of patients with Neuroendocrine Carcinomas

The human hormone somatostatin was initially identified as a hypothalamic inhibitor of growth hormone.⁸ It was subsequently discovered to be a universal endocrine “off switch” due to its exocrine, endocrine, paracrine and autocrine inhibitory effects.⁹ In the digestive tract, it reduces secretion and motility, decreases portal blood flow, and reduces the secretion of other gastrointestinal hormones. The effects of somatostatin are mediated through interaction with five somatostatin receptors (sst₁₋₅), belonging to a family of G-protein coupled receptors with seven transmembrane domains.¹⁰

The clinical use of native human somatostatin is limited by its short half life of approximately two minutes. In order to improve the pharmacokinetic profile, synthetic somatostatin analogs (SSAs) have been developed by shortening the polypeptide chain while retaining binding affinity to somatostatin receptors.¹¹ The two commercially available analogs, octreotide and lanreotide, are octapeptides that bind with high affinity to somatostatin receptor 2 (sst₂) and with moderate affinity to sst₅.

Octreotide has been used in clinical practice since the 1980s when it was shown to effectively palliate the carcinoid syndrome, as well as other syndromes caused by metastatic neuroendocrine tumors including VIPomas and glucagonomas. Octreotide was initially available in an immediate-release subcutaneous formulation. During the past decade, a long-acting repeatable (LAR) depot formulation of octreotide (Sandostatin LAR) has been available allowing for monthly intramuscular dosing.¹²

In recent years, evidence of the antineoplastic activity of SSAs has emerged. Although objective radiographic responses associated with these agents are rare, many cases of prolonged disease stability have been documented in the literature, leading to the hypothesis that SSAs exert an inhibitory effect on tumor growth. Last year, results of a phase III randomized, placebo-controlled study, the PROMID trial, were published. In this trial, 85 patients with well-differentiated carcinoid tumors originating in the distal intestine and proximal colon (midgut) were randomized to receive either octreotide LAR 30 mg or placebo. Median progression-free survival was 14.3 months in the octreotide LAR group versus 6.0 months in the placebo group (p=0.000072), confirming the antiproliferative effect of octreotide in this patient population.⁵

Pasireotide (SOM230) is a novel somatostatin analog with a similar binding affinity to somatostatin sst₂ and substantially stronger binding affinities to ssts₁, ₃ and ₅ (see section 1.3).¹³ Preclinical data suggests that ssts₁, ₃ and ₅ play an important role in cell cycle arrest and induction of apoptosis.¹⁴ Thus, we hypothesize that pasireotide LAR may prove to be a more potent inhibitor of neuroendocrine tumor proliferation than octreotide LAR.

1.3 Pasireotide (SOM230)

Pasireotide is an injectable somatostatin analogue. It is a novel cyclohexapeptide with the following chemical name: (2-Aminoethyl)carbamic acid (2R,5S,8S,11S,14R,17S,19aS)-11-(4-aminobutyl)-5-benzyl-8-(4-benzyloxybenzyl)-14-(1H-indol-3-ylmethyl)-4,7,10,13,16,19-hexa-oxo-17-phenyloctadecahydro-3a,6,9,12,15,18-hexaazacyclopentacyclooctadecen-2-yl ester, di[(S)-2-aminosuccinic acid] salt.

Like natural somatostatin and other somatostatin analogues (SSAs), pasireotide exerts its pharmacological activity via binding to somatostatin receptors (sst_s). There are five known somatostatin receptors: sst₁₋₅. Somatostatin receptors are expressed in different tissues under normal physiological conditions. Somatostatin analogues activate these receptors with different potencies¹⁵ and this activation results in a reduced cellular activity and inhibition of hormone secretion. Somatostatin receptors are strongly expressed in many solid tumors, especially in neuroendocrine tumors. The SSAs currently approved for use in the clinic (octreotide and lanreotide) have a high affinity to the sst₂, with moderate or no affinity to the remaining subtypes. Pasireotide is a novel cyclohexapeptide somatostatin analogue that exhibits a unique binding profile, binding with high affinity to four of the five known human somatostatin receptors. (Table 1.1). Compared to Sandostatin[®] (octreotide acetate), pasireotide exhibits a binding affinity which is 30-40 times higher for human sst₁ and sst₅, 5 times higher for human sst₃, and 2.5 times lower for human sst₂. A detailed summary of available preclinical data is provided in the Investigators' Brochure.

Table 1.1 Binding profile for octreotide and pasireotide at sst₁₋₅ (IC₅₀, M)

Compound	sst 1	sst2	sst3	sst4	sst5
octreotide	2.8x10 ⁻⁷	3.8x10 ⁻¹⁰	7.1x10 ⁻⁹	>10 ⁻⁶	6.3x10 ⁻⁹
Pasireotide	9.3x10 ⁻⁹	1.0x10 ⁻⁹	1.5x10 ⁻⁹	>10 ⁻⁶	1.6x10 ⁻¹⁰
Ratio of IC ₅₀ : octreotide to pasireotide	30	0.4	5	--	40

Additionally, preclinical studies suggest anti-tumor activity of pasireotide. Pasireotide has been found to significantly reduce cell proliferation of the neuroendocrine tumor cell line NCI-H727, whereas the conventional analogue octreotide did not.¹⁶

1.4 Clinical experience with pasireotide

Pasireotide is available as a short-acting subcutaneous (s.c) formulation and a long acting release (LAR) intramuscular (IM) formulation.

1.4.1 Pasireotide s.c.

Pasireotide when given subcutaneously (s.c.) was well-tolerated at doses up to 600 µg b.i.d., 900 µg b.i.d. and 1200 µg b.i.d by acromegalic, Cushing's disease and carcinoid tumor patients, respectively. In addition, healthy volunteers have received pasireotide s.c. as a continuous infusion for seven days with total daily doses of up to 2025 µg being well tolerated. For all indications the most frequently reported adverse events were gastrointestinal, predominantly diarrhea, nausea and abdominal pain. Generally these events were mild, transient and only occasionally caused patients to discontinue treatment.

Hyperglycemia was also observed for patients in all three indications. In general HbA1c was observed to increase by approximately 1%, corresponding to a blood glucose increase of approximately 30 mg/dL. Blood glucose increases tended to occur with increasing dose, and appeared to be more notable in patients who had a history of hyperglycemia or diabetes mellitus prior to receiving pasireotide. However hyperglycemia in these patients was responsive to appropriate diabetic management such as adjustments in oral antidiabetic treatment, or in some cases the addition of insulin.

Occasionally laboratory abnormalities in liver function tests and pancreatic enzymes have been observed at higher doses of pasireotide. These events however have been transient.

Further details on pasireotide s.c. can be found in the Investigator Brochure.

1.4.1.1 Phase II studies of pasireotide s.c. in neuroendocrine tumors

Preliminary safety data are available from a Phase II study [CSOM230B2202] in 45 patients with symptomatic metastatic carcinoid disease who received pasireotide s.c. doses from 300 µg s.c. b.i.d. up to 1200 µg b.i.d. for a mean of 20 weeks. Overall pasireotide s.c. has been found to be generally well-tolerated by these patients, with the most common adverse events being mild diarrhea, nausea and abdominal pain. Blood glucose increases tended to occur with increasing dose, but were moderate and generally managed easily by adjustment in oral hypoglycemic medications. Weight loss was also observed in 18 patients. Maximum weight loss occurred within 4 to 6 months on the study drug, with a stabilization of effect after approximately 6 months. There was no apparent relationship between the weight loss and pasireotide dose.

Preliminary efficacy data from this study also support that pasireotide is active in patients refractory/resistant to Sandostatin LAR, as partial or complete symptom control was observed in 12 of 44 patients (27%). Complete symptomatic response was achieved in two patients at the pasireotide 600 µg s.c. b.i.d. dose and one at the 900 µg s.c. b.i.d. dose. Nine patients achieved partial symptomatic response to treatment, three at each of the following doses: 600, 750, 900 µg s.c. b.i.d.

1.4.2 Pasireotide LAR

Most of the experience with pasireotide comes from healthy volunteer and patient studies evaluating the subcutaneous formulation of pasireotide. Pasireotide LAR is being evaluated in two studies, one healthy volunteer study and one study involving patients with acromegaly and carcinoid disease.

1.4.2.1 Pasireotide LAR in healthy volunteers

Preliminary data from the healthy volunteer study found single IM doses of pasireotide LAR, at doses of up to 40 mg and 60 mg, respectively to be well-tolerated. The most common adverse events were gastrointestinal. Diarrhea was experienced by most of the subjects and was sometimes associated with abdominal pain, flatulence, and/or nausea. The gastrointestinal events were mild or moderate in severity. About 38% of subjects reported mild injection site pain and about 15% reported headaches.

Transient elevations in liver function tests and/or pancreatic enzymes were observed in two subjects, both of which resolved and were not accompanied by any clinical symptoms. Mild increases in fasting blood glucose were observed in some subjects during the pasireotide LAR treatment period. All elevations were asymptomatic, considered not clinically significant and generally returned to normal within 3 to 4 weeks after the pasireotide LAR IM injection.

1.4.2.2 Pasireotide LAR in acromegalic patients

Preliminary safety data are available from 18 acromegalic patients treated with pasireotide LAR in an ongoing study [CSOM230C2110]. These patients had received pasireotide LAR at doses of 20 (n=5), 40 (n=6) or 60 mg (n=7) for about six weeks at the time of the summary. Pasireotide LAR was well-tolerated by acromegalic patients in this study. The most common drug-related adverse events were gastrointestinal, predominantly diarrhea. Mild erythema reported as drug-related was experienced by three patients. Two patients on the 60 mg dose were reported to experience drug-related increases in blood glucose: mild diabetes mellitus was reported for one patient and mild hyperglycemia was reported for the other patient who also had a history of diabetes mellitus at baseline. A further patient who received the 20 mg dose experienced hyperglycemia, however this event was considered to be unrelated to study drug by the investigator. All three patients were given oral hypoglycemic agents and all continued in the trial.

Following 2-3 injections of pasireotide LAR in acromegaly patients [CSOM230C2110], steady-state concentrations of pasireotide were achieved. The trough plasma concentrations of pasireotide at steady state ($C_{min,ss}$) on day 84 were 3.8 ± 2.1 , 5.6 ± 2.4 , and 13.8 ± 10.2 ng/mL for 20 mg (N=9), 40 mg (N=9), and 60 mg (N=11) LAR, respectively, indicating an approximate dose proportionality.

The primary purpose of the study is to investigate the progression-free survival associated with pasireotide LAR in treatment-naïve patients with metastatic carcinoid and pancreatic neuroendocrine tumors.

Secondary objectives are to assess the overall survival (OS) associated with pasireotide LAR, overall radiographic response rate (ORR), adverse events (AEs), changes in tumor markers and changes in quality of life (QOL).

2.1 Selection of doses

Based on the tolerable side-effect profile of pasireotide LAR at doses of 60mg every 4 weeks (see section 1.4.2.3) and pharmacokinetic data demonstrating therapeutic drug levels at that level, the dose of pasireotide in this study will be 60mg IM every 4 weeks. No doses of pasireotide LAR exceeding 60mg will be tested in this trial. If tolerability issues occur, the treatment dose may be reduced to 40mg.

3 Endpoints

3.1 Primary endpoints

- Progression-free survival (PFS)
- Rate of PFS at one year

3.2 Secondary endpoints

- Overall survival (OS)
- Overall radiographic response rate (ORR)
- Adverse events (AEs)
- Changes in neuroendocrine tumor markers (such as chromogranin A or pancreatic polypeptide), or hormonal assays (such as urine 5-HIAA, gastrin, insulin, glucagon, vasoactive intestinal peptide, etc) if elevated at baseline.
- Changes in quality of life (as measured by EORTC questionnaires EORTC QLQ-C30 and QLQ GI.NET21)

3.3 Exploratory endpoint

- To assess the correlation between somatostatin receptor profiling (via immunohistochemistry) and PFS

4 Study design

This is a multi-institutional, prospective phase II open-label trial.

4.1 Treatment

The investigational drug used in this study is pasireotide LAR 60mg. Pasireotide will be administered as an intramuscular injection at the beginning of every cycle which is defined as 28 days (+/- 3 days). Study treatment should begin within 14 days following enrollment into the study and continue until disease progression, unacceptable toxicity, or withdrawal of consent. Safety and efficacy will be assessed throughout the treatment period.

4.1.1 Rescue treatment for diarrhea and other breakthrough hormonal symptoms

Patients with hormonal symptoms caused by neuroendocrine tumors (such as the carcinoid syndrome) may experience symptom flares requiring short-acting rescue medications. For these patients, short-acting pasireotide sc may be prescribed at the discretion of the investigator at a dose of 600 mcg bid prn. Patients who continue to experience breakthrough diarrhea due to carcinoid syndrome or other hormonal syndromes may use antidiarrheal medications such as loperamide or diphenoxylate and atropine. SOM230 may

cause malabsorption and steatorrhea which can be controlled with pancreatic enzyme supplementation.

4.2 Follow-up

All patients will be followed for adverse events and serious adverse events for 28 days following the last dose of pasireotide, or until resolution or stabilization of the event, whichever comes first.

5 Population

The study population will consist of patients with advanced (metastatic or unresectable) well and moderately differentiated neuroendocrine tumors of the gastrointestinal tract and lungs (carcinoid tumors) and pancreatic neuroendocrine tumors.

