6.3 Follow-up for toxicities

Patients who interrupt or permanently discontinue pasireotide due to an adverse event or abnormal laboratory value must be followed at least weekly for 28 days after the last dose of pasireotide, and subsequently at monthly intervals until resolution or stabilization of the event,

whichever comes first. If a patient requires a dose delay of > 21 days from the intended day of the next scheduled dose, then the patient should be discontinued from the study.

All patients will be followed for adverse events and serious adverse events for 28 days following the last dose of pasireotide.

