6.4 End of treatment

Patients may voluntarily withdraw from the study or be dropped from it at the discretion of the investigator at any time. Patients will be withdrawn from the study if any of the following occur:

- Disease progression
- Death
- Withdrawal of consent
- Delay of treatment >21 days.
- Uncontrolled diabetes mellitus (DM)
- Pregnancy
- Adverse event(s) \geq grade 3 despite dose reduction
- QTc prolongation (see section 6.3.2)

7 Visit schedule and assessments

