7.3 End of Treatment Evaluation

Data to be obtained at completion of study:

- Physical examination
- Toxicity assessment
- Vital signs
- Weight
- ECOG PS
- CBC with differential
- Comprehensive metabolic panel
- Glycosylated hemoglobin
- ECG
- Assessment of adverse events
- Radiologic assessment of tumor burden (if patient is discontinued for any reason other than radiographic disease progression).

Table 7-3 lists all of the assessments and indicates the visits at which they are to be performed with an “X”. All data obtained from these assessments must be supported in the patient’s source documentation.

Table 7-3 Visit evaluation schedule

Evaluation	Screening/ Baseline^a	6 hours after 1st injection, 21 days after 1st and 3rd injections	Each Cycle (day 1)^k	Cycle 6	Every 3 Cycles	End^b
Informed consent	X					
Demographics	X					
Relevant medical history/ current medical conditions	X		X			X
Diagnosis and extent of cancer	X					
Physical exam	X		X			X
Vital signs	X		X			X
ECG ^c	X	X		X	X	X
LFT testing		X				
ECOG Performance Status	X		X			X
CBC with differential ^d	X		X			X
Glycosylated hemoglobin	X					X
Fasting	X		X			X

Comprehensive metabolic panel ^e						
Pregnancy test and review of contraception ^f	X					X
Secretory hormones ^g and serum chromogranin A	X				X	
Radiologic assessment of tumor burden ^h	X				X	X
Adverse events ⁱ	X		X			X
Concomitant medications ^j	X		X			X
EORTC QLQ C-30 and EORTC QLQ GI-NET21 questionnaires	X				X	

^a Screening includes review of: demography/informed consent, inclusion/exclusion criteria, relevant medical history/concomitant medications, diagnosis and extent of cancer.

^b Patients who interrupt or permanently discontinue pasireotide due to an adverse event or abnormal laboratory value must be followed at least weekly for 28 days after the last dose of SOM230, and subsequently at monthly intervals until resolution or stabilization of the event, whichever comes first.

^c All ECGs should be done before SOM230 injection on the same day. ECG should be done at any time when clinically indicated.

^d Complete blood count must include: hemoglobin, hematocrit, platelets, total white blood cell count and differential.

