9.1.2 Recordati Inc. instructions for rapid notification of serious adverse events

The principal investigator has the obligation to report all serious adverse events to the FDA, IRB, and Recordati Inc. Pharmaceuticals Integrated Medical Safety (IMS).

All events reported to the FDA by the investigator are to be filed utilizing the Form FDA 3500A (MedWatch Form).

All events must be reported, by [contact]), to Recordati Inc. Pharmaceuticals IMS Department within 24 hours of learning of its occurrence. This includes serious, related, labeled (expected) and serious, related, unlabeled (unexpected) adverse experiences, all deaths during treatment or within 30 days following completion of active protocol therapy.

Any serious adverse event occurring after the patient has provided informed consent and until 4 weeks after the patient has stopped study participation must be reported. This includes the period in which the study protocol interferes with the standard medical treatment given to a patient (e.g. treatment withdrawal during washout period, change in treatment to a fixed dose of concomitant medication).

Serious adverse events occurring more than 4 weeks after study discontinuation need only be reported if a relationship to the Recordati Inc. study drug (or therapy) is suspected.

For Comparator Drugs/Secondary Suspects (Concomitant Medications), all serious adverse experiences will be forwarded to the product manufacturer by the investigator.

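### Overall survival is a secondary endpoint, but patients leave the study at progression, with no survival follow-up, OS definition or censoring rule

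*Combined protocol and SAP*

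**What the plan says.** - **Objective and endpoint.** Section 2 states: "Secondary objectives are to assess the overall survival (OS) associated with pasireotide LAR". Section 3.2 lists OS first among the secondary endpoints, by name only.
- **Leaving the study.** Section 6.4 states: "Patients will be withdrawn from the study if any of the following occur". Disease progression heads the list. Section 6.3 says of a dose delay over 21 days: "then the patient should be discontinued from the study".
- **After the last dose.** Section 4.2 states: "All patients will be followed for adverse events and serious adverse events for 28 days following the last dose of pasireotide". It lets this end earlier if the event resolves or stabilises. Under section 6.3, patients who interrupt or stop because of an adverse event or abnormal laboratory value are seen weekly for 28 days, and "subsequently at monthly intervals until resolution or stabilization of the event".
- **Last visit.** Section 7.3 lists "Data to be obtained at completion of study", and Table 7-3 stops at the End column.
- **Deaths.** Section 9.1.2 covers "all deaths during treatment or within 30 days following completion of active protocol therapy". It also requires SAE reports until 4 weeks after participation stops; later SAEs are reported only if a link to the drug is suspected.
- **Analysis.** Section 8 defines PFS twice and gives it a censoring table (Table 8.4). Neither section 8 nor section 11 mentions OS.

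**The concern.** OS needs each patient's vital status until death or a common cut-off, whatever happens to treatment. This plan ties observation to treatment. A patient who progresses goes off study and is last known alive about a month later, while most deaths in this disease can be expected after progression.

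Two problems follow. Few deaths are recorded, so any OS estimate is imprecise. And censoring happens just as prognosis probably worsens, so a Kaplan-Meier curve largely carries the pre-progression death rate forward and tends to read too high. In a single-arm trial, readers may set that figure beside outside data. With no stated time origin or censoring rule, sites and analysts could also handle OS differently.

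**Working it through.** **No OS figure to reproduce.** The documents state no OS median, event count or follow-up length. The inputs from the plan are n = 35 (section 11.1) and median PFS of 5 months (null) and 9 months (alternative) (section 11.2). Everything else below is an assumption.

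**Base model.** Exponential PFS.

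- q = share of first PFS events that are deaths, 2% to 10% (assumed).
- m = median survival after progression, 12 to 51 months (assumed).
- Observation ends 28 days (0.92 months) after progression. This matches the 4 weeks from stopping participation in section 9.1.2; section 4.2 counts from the last dose.

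*Share of all eventual deaths that is observed* = q + (1 − q)(1 − 2^(−0.92/m)). It does not depend on PFS.

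| q | m = 12 | m = 51 |
|---|---|---|
| 2% | 7.1% | 3.2% |
| 5% | 9.9% | 6.2% |
| 10% | 14.7% | 11.1% |

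Times 35, this is 1.1 to 5.1 deaths, so 85% to 97% of eventual deaths are missed.

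*36-month horizon and 24-month OS.* Let λ = ln 2 / median PFS and μ = ln 2 / m. True survival is S(t) = e^(−λt) + (1 − q)·λ/(λ − μ)·(e^(−μt) − e^(−λt)).

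Example with median PFS 9, q = 5%, m = 27: λ = 0.0770 and μ = 0.0257.

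- S(24) = 0.158 + 1.425 × (0.540 − 0.158) = 0.70.
- S(36) = 0.0625 + 1.425 × (0.397 − 0.0625) = 0.539, so full follow-up sees 35 × 0.461 = 16.1 deaths.

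The as-written columns come from 1,000,000 simulated patients with median PFS 9 months:

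| q, m | Deaths by 36 months: full / as written | 24-month OS: true / Kaplan-Meier as written |
|---|---|---|
| 2%, 12 | 24.2 / 2.3 | 52.0% / 88.4% |
| 5%, 27 | 16.1 / 2.4 | 70% / 88% |
| 10%, 51 | 11.8 / 3.6–3.7 | 77.4% / 82.4% |

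Over the whole grid, full follow-up sees 10 to 25 deaths against 1.1 to 4.8 as written (69% to 91% lost), and 24-month OS is overstated by 5 to 36 points.

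At median PFS 5 months the overstatement runs from about 0 points (q = 10%, m = 51: true 72.1%, estimated 71.8%) to 41 points (q = 2%, m = 12: 39.5% against 80.5%).

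**Bound favourable to the plan.** Assume the same death hazard before and after progression, with median OS 24 to 60 months. Then q = median PFS / median OS.

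- PFS 9, OS 24: q = 0.375; share = 0.375 + 0.625 × (1 − 2^(−0.92/24)) = 0.391, or 13.7 of 35. By 36 months: 12.9 recorded against 35 × (1 − 2^(−36/24)) = 22.6 (43% lost).
- PFS 5, OS 60: q = 0.083; share = 0.093, or 3.3 of 35. By 36 months: 3.2 against 11.9 (73% lost).

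Here Kaplan-Meier is imprecise but not biased.

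**Separate check.** Independent exponential times to progression and to death, with observation ending 1 month after progression, median OS 24 to 60 months and cut-off at 24 to 60 months, capture 18% to 54% of the deaths. Independence probably overstates capture.

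**The case against.** The strongest reply is that section 6.4 is headed as end of treatment and lists death as a ground for withdrawal, so it may use study and treatment loosely. Section 8.1 asks sites to try to document progression after treatment stops, and Table 8.4 dates deaths after one or two missed visits, so some data beyond attended visits are expected. This stands as a point about wording: the text can be read as silent rather than as an instruction to stop observing. It does not supply follow-up. The section 8.1 note and Table 8.4 serve PFS, and the monthly visits in section 6.3 follow an unresolved event, not vital status.

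The second reply is that the size is assumed. That is right. The documents support neither q nor m, the 85% to 97% figure uses an unlimited horizon, and the bias can be near zero in some settings. The direction is plausible; the amount is not established.

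Third, OS has no hypothesis, alpha or comparator in a 35-patient single-arm trial, and the PFS time origin could be carried over. This limits the severity but leaves a named objective unanswered.

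Fourth, the schedules for patients on therapy beyond 5 years suggest, without proving, that the trial is mature. Prospective calls would then miss patients already off study.

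**Conclusion.** The concern holds. OS is promised, but the plan neither collects the deaths needed nor defines the endpoint. Every scenario examined loses a large share of deaths: at 36 months, 69% to 91% in the base model with median PFS 9 months, and 43% to 73% under equal hazards. Upward bias depends on a higher death risk after progression. In the base model it ranges from about 0 to 41 points at 24 months across the two PFS medians in section 11.2. These sizes rest on assumed values; the gap itself rests on the text alone. The damage is confined to this secondary endpoint, and the primary 12-month PFS analysis is untouched. It should be corrected, but it does not threaten the main conclusion.

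**What to change.** 1. **Sections 4.2 and Table 7-3:** add a periodic vital-status check by telephone or record review after the End visit, until death, withdrawal of consent or study close. Every 12 weeks is one example; the interval is the sponsor's choice.
2. **Sections 6.3 and 6.4:** separate stopping study treatment from leaving the study, so that patients off treatment stay in survival follow-up unless they withdraw consent. No treatment-stopping rule changes.
3. **Section 8:** define OS as time from first study treatment to death from any cause, censored at the date last known alive and not at progression or new anticancer therapy. **Section 11:** state that OS is described by Kaplan-Meier with the number of deaths.
4. **If follow-up is not feasible:** delete OS from sections 2 and 3.2.

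**Cost:** an amendment, consent wording and a brief contact or chart check per patient per quarter, with no added imaging or procedures. Patients already off study would need retrospective ascertainment from records and possibly renewed consent. Option 4 costs only the amendment.
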